#### **Additional Procedures for the Intervention Group Only [Week 8 (Visit 11)]**

- If applicable, perform pregnancy test (Section 6.7)
- Investigational Product Intravitreal Injection (Section 6.11)
- Dispense artificial tears and/or lubricating ointment (Section 6.12)
- Perform Pre-Injection Assessment (Section 6.13)

### **7.12. Week 10 (Visit 12) Intervention Group Only**

- Collect adverse events (Sections 6.6 and 8)
- Collect concomitant medications (Section 6.5)
- If applicable, perform pregnancy test (Section 6.7)
- Investigational Product Intravitreal Injection (Section 6.11)
- Dispense artificial tears and/or lubricating ointment (Section 6.12)
- Perform Pre-Injection Assessment (Section 6.13)

### **7.13. Week 12 (Visit 13)**

- Perform Routine Clinical Ophthalmic Follow-up examination (Section 6.8.3)
- Endpoint evaluation by Evaluating Investigator (Section 6.8.4)
- Perform BCVA (Section 6.8.1)
- Perform IOP (Section 6.8.2)
- Collect Fundus Photographs (Section 6.8.5)

- Collect Macular Optical Coherence Tomography (Section 6.8.6)
- Collect adverse events (Sections 6.6 and 8)
- Collect concomitant medications (Section 6.5)

**Additional Procedures for the Intervention Group Only [Week 12 (Visit 13)]**

- If applicable, perform pregnancy test (Section 6.7)
- Investigational Product Intravitreal Injection (Section 6.11)
- Dispense artificial tears and/or lubricating ointment (Section 6.12)
- Perform Pre-Injection Assessment (Section 6.13)

**7.14. Week 14 Visit (14) Intervention Group Only**

- Collect adverse events (Sections 6.6 and 8)
- Collect concomitant medications (Section 6.5)
- If applicable, perform pregnancy test (Section 6.7)
- Investigational Product Intravitreal Injection (Section 6.11)
- Dispense artificial tears and/or lubricating ointment (Section 6.12)
- Perform Pre-Injection Assessment (Section 6.13)

**7.15. Week 16 (Visit 15)**

- Perform Routine Clinical Ophthalmic Follow-up examination (Section 6.8.3)
- Endpoint evaluation by Evaluating Investigator (Section 6.8.4)
- Perform BCVA (Section 6.8.1)
- Perform IOP (Section 6.8.2)
- Collect Fundus Photographs (Section 6.8.5)
- Collect Macular Optical Coherence Tomography (Section 6.8.6)
- Collect adverse events (Sections 6.6 and 8)
- Collect concomitant medications (Section 6.5)

**Additional Procedures for the Intervention Group Only [Week 16 (Visit 15)]**

- If applicable, perform pregnancy test (Section 6.7)
- Investigational Product Intravitreal Injection (Section 6.11)
- Dispense artificial tears and/or lubricating ointment (Section 6.12)
- Perform Pre-Injection Assessment (Section 6.13)

### **7.16. Week 24 (Visit 16)**

- Collect vital signs
- Perform physical examination (Section 6.4)
- Collect adverse events (Sections 6.6 and 8)
- Collect concomitant medications (Section 6.5)
- Collect samples for safety labs, urinalysis, and pregnancy test, if applicable (Section 6.7)
- Perform Routine Clinical Ophthalmic Follow-up examination (Section 6.8.3)
- Endpoint evaluation by Evaluating Investigator (Section 6.8.4)
- Perform BCVA (Section 6.8.1)
- Perform IOP (Section 6.8.2)
- Collect Fundus Photographs (Section 6.8.5)
- Collect Macular Optical Coherence Tomography (Section 6.8.6)

## **8. ADVERSE EVENT REPORTING**

AEs will be collected from the time the subject signs the informed consent form through 30 days after the last IP administration.

### **8.1. Adverse Event**

An AE is any untoward medical occurrence in a patient administered an IP, which does not necessarily have a causal relationship with the IP treatment. Therefore, an AE can be any unfavorable and unintended sign (including an abnormal laboratory finding), symptom, or disease temporally associated with the use of the IP, whether or not it is considered related to the IP.

Abnormal laboratory and other abnormal investigational findings (i.e., physical exam) should not be reported as AEs unless they are associated with clinical signs and symptoms, lead to treatment discontinuation, or are otherwise considered clinically relevant by the investigator. In cases of surgical or diagnostic procedures, the condition/illness leading to such a procedure is considered as the AE rather than the procedure itself. In case of a fatality, the cause of death is considered as the AE, and the death is considered as its outcome.

### **8.2. Events Not to Be Considered as Adverse Events**

Pre-existing medical conditions/signs/symptoms present before the Screening Visit (Visit 1) that do not worsen in severity or frequency during the clinical trial are defined as baseline medical conditions and are not to be considered AEs.

Pregnancies are not considered AEs but must be reported, see Section 8.7.

Recurrent retinal detachments (and subsequent treatments) are a clinical endpoint of the clinical trial. They will not be captured as AEs/SAEs.

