### **2.2. Clinical Trial Endpoints**

#### **2.2.1. Primary Endpoints**

The primary endpoint in Part 1 and Part 2 is recurrent retinal detachment requiring reoperation within 24 weeks from time of enrollment. An evaluating investigator should determine whether the primary endpoint has been met. The primary endpoint requires verification by the Central Reading Center (CRC) before recurrent retinal detachment reoperation. In cases where CRC verification is not possible due to technical limitations with the Optical Coherence Tomography or fundus photograph, then the evaluating investigator will contact the trial medical monitor to confirm whether the primary endpoint has been met. These verification processes provide an additional level of objectivity in end point evaluation.

Definition of recurrent retinal detachment (defined as either one OR both of the following):

1. Spectral-Domain Optical Coherence Tomography (SD-OCT) demonstrating fovea-off retinal detachment (subfoveal fluid that is contiguous with a peripheral detachment);
2. Color fundus photographic documentation of a rhegmatogenous or tractional (or undetermined) retinal detachment that has progressed posterior to the Mandatory Reoperation Zone, as defined as defined by a circle centered on the fovea, with a radius halfway between the arcades and the equator (Figure 2).

Stable, peripheral rhegmatogenous or tractional (or undetermined) detachments anterior to the mid-periphery may be observed or demarcated with laser at the investigator's discretion and will not be counted as failure.

Subjects who have retinal detachment within 1-week post-operatively will be deemed to have failed Day 0 (day of surgery) and will be removed from the efficacy analysis. These will be considered "dropped" subjects. Subjects receiving investigational product during this period will continue to be followed for safety. Retinal detachment is defined as subjects who meet either of the recurrent retinal detachment imaging criteria as defined in the Primary Endpoint.

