### **2.2.3. Exploratory Endpoints**

Exploratory endpoints in Part 1 and Part 2 include:

1. Total number of vitrectomy surgeries performed by Week 24
2. Total retinal attachment at Week 24
3. Total macular attachment at Week 24
4. Central macular thickness (as measured by SD-OCT) at Week 24
5. Macular epiretinal membrane (as visualized by SD-OCT) at Week 24
6. Macular and extramacular epiretinal membrane visible on color fundus photographs at Week 24
7. Percentage of eyes with intraocular pressure (IOP) < 5 mmHg at Week 24

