#### **4.3. Subject Withdrawal**

If intraoperative complete retinal reattachment is not achieved, subjects will not complete enrollment. These subjects will be dropped from enrollment and will be noted as screen failures.

Subjects who have retinal detachment within 1-week post-operatively will be deemed to have failed Day 0 (day of surgery) and will be removed from the efficacy analysis. These will be considered “dropped” subjects. Subjects receiving investigational product during this period will continue to be followed for safety.

Subjects will be removed from the clinical trial if they develop infectious endophthalmitis and/or no light perception vision.

Subjects may also be removed at the discretion of the principal investigator or at the wishes of the subject himself/herself.

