## **8.6. Serious Adverse Events**

An SAE is any AE that results in any of the following outcomes:

- death;
- a life-threatening AE;
- Note: An AE is considered “life-threatening” if, in the view of either the investigator or Sponsor/designee, the subject is at immediate risk of death as a result of the AE.

■ "Life-threatening" does not include an AE that, had it occurred in a more severe form, might have caused death.

- inpatient hospitalization or prolongation of existing hospitalization;
  - Note: The term "inpatient hospitalization" refers to any inpatient admission (even if less than 24 hours). For chronic or long-term subjects, inpatient admission includes transfer within the hospital to an acute/intensive care inpatient unit. Inpatient hospitalization does not include emergency room visits; outpatient/same-day/ambulatory procedures; or admission to observation/short-stay units, rehabilitation facilities, hospice facilities, nursing homes, or clinical research/Phase 1 units.
  - Note: The term "prolongation of existing hospitalization" refers to any extension of an inpatient hospitalization beyond the stay anticipated or required for the reason for the initial admission, as determined by the investigator or treating physician.
- a persistent or significant incapacity or substantial disruption of the ability to conduct normal life functions;
  - Note: A serious adverse event (SAE) specifically related to visual threat would be interpreted as any potential impairment or damage to the subject's eyes (e.g., hemorrhage, retinal detachment, central corneal ulcer, or damage to the optic nerve).
- a congenital anomaly/birth defect; and,
- other serious (Important Medical Events) events that do not fit other outcomes, where the event may jeopardize the subject and may require medical or surgical intervention to prevent one of the outcomes listed in the SAE definition, based upon appropriate medical judgment.

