## **9. STATISTICS HYPOTHESES AND METHODS OF ANALYSES**

### **9.1. Clinical Trial Populations**

#### **9.1.1. Intent-to-Treat (ITT)**

The Intent-to-Treat (ITT) population consists of all subjects who were randomized. All data will be included, and no subjects will be excluded because of protocol violations. All data will be included, and no subjects will be excluded because of protocol violations; subjects who have retinal detachment within 1-week post-operatively who will be deemed to have failed Day 0 (surgery) and will be removed from the efficacy analysis as per protocol per Section 2.2.1.

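### Retinal detachments in the first post-operative week are excluded from both AE/SAE recording and the efficacy analysis, and the protocol plans no count of them as events

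*Combined protocol and SAP*

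**What the plan says.** Four parts of the protocol bear on this point.

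- **AE/SAE recording.** Section 8.2 states: "Recurrent retinal detachments (and subsequent treatments) are a clinical endpoint of the clinical trial. They will not be captured as AEs/SAEs". It sets no limit by timing and does not require that the event be counted in an analysis.
- **SAE definition.** The note on visual threat in Section 8.6 gives these examples: "e.g., hemorrhage, retinal detachment, central corneal ulcer, or damage to the optic nerve".
- **First-week detachments.** Under Section 2.2.1 these subjects "will be deemed to have failed Day 0 (day of surgery) and will be removed from the efficacy analysis". The same section fixes what counts: "Retinal detachment is defined as subjects who meet either of the recurrent retinal detachment imaging criteria as defined in the Primary Endpoint". Sections 4.3, 4.4 and 9.4.5 repeat the removal, and the ITT definition in Section 9.1.1 builds it in, saying such subjects "will be removed from the efficacy analysis as per protocol per Section 2.2.1". On safety, Section 4.3 says: "Subjects receiving investigational product during this period will continue to be followed for safety".
- **Stable peripheral detachments.** Section 2.2.1 allows observation or laser demarcation at the investigator's "discretion and will not be counted as failure". Section 2.2.3 separately lists the exploratory endpoint "Total retinal attachment at Week 24".

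**The concern.** Keeping endpoint events out of AE reporting is common and avoids double counting. It is justified because the event is captured elsewhere, in the efficacy data. For first-week detachments that justification fails: the exemption in Section 8.2 still applies, but the efficacy count it relies on has been removed.

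These are serious events in eyes that have already been dosed. Section 6.11 places the first injection on Day 0 or Day 1. Under the visit note in Section 7, Week 1 can begin on the Monday after a Friday Day 1, so a second injection can also fall within seven days of surgery. A detachment in that window may well be surgical failure, as the protocol presumes, but the presumption is never tested case by case. Without an AE record there is no investigator judgement of relatedness or expectedness (Section 8.4) and no 24-hour report (Section 8.6.2).

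Since Version 5.0 every new subject receives drug. Part 1b therefore has no concurrent control arm in which an excess of early detachments could show, so complete capture in treated eyes matters more.

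**Working it through.** The plan gives no figure on this point. Its only calculated figure, the original Part 1 sample size, does not bear on it. The check is mainly a matter of following each kind of study-eye detachment through the text.

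**1. Does Section 8.2 reach first-week detachments?** Section 2.2.1 defines them by the same two imaging criteria as recurrent detachment. Inclusion criterion 5 (Section 3.6.1) requires a fully attached retina at the end of surgery, so a later detachment in that eye is a recurrence in the ordinary sense too. On both grounds Section 8.2 applies.

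**2. Where would each kind be counted?**

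| Study-eye detachment | AE/SAE record | Primary analysis | Other planned output |
|---|---|---|---|
| After week 1, meets imaging criteria, needs reoperation | Barred by 8.2 | Counted | Vitrectomy count, Week 24 attachment |
| Within week 1, meets imaging criteria | Barred by 8.2 | Removed | No event count planned; may show as a dropped subject in disposition or in ophthalmoscopy data |
| Stable, peripheral | Unclear: outside the defined term | Subject stays in; not a failure | Should show under Week 24 total attachment if still present |

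Only the second row has neither a safety record nor an efficacy count. The vitrectomy count by Week 24 would help there only if removal from the efficacy analysis does not extend to exploratory endpoints, which the text does not settle.

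**3. How do Sections 8.2 and 8.6 compare?** One says a recurrent detachment is not captured as an SAE. The other names retinal detachment as an example of an SAE. Neither refers to the other, so a site with a first-week case is not told which governs.

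**4. How large could the gap be?** The protocol gives neither a first-week rate nor the historical control rate. Assume 100 treated eyes and k first-week detachments, with about 20% of the remaining eyes detaching later. The 20% is the original design rate for drug in Section 9.3.1. With x events in n eyes, the exact 95% upper bound is the 0.975 quantile of Beta(x + 1, n − x). The protocol names no interval method, so the exact one is also an assumption.

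| k | First-week eyes removed | Upper bound | First-week eyes counted | Upper bound | Difference in bounds |
|---|---|---|---|---|---|
| 2 | 20/98 = 20.4% | 29.7% | (20 + 2)/100 = 22.0% | 31.4% | about 2 points |
| 5 | 19/95 = 20.0% | 29.5% | (19 + 5)/100 = 24.0% | 33.6% | about 4 points |
| 10 | 18/90 = 20.0% | 29.8% | (18 + 10)/100 = 28.0% | 37.9% | about 8 points |

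The removed eyes barely alter the reported rate, so the primary result will not reveal how many there were. The table shows only how visible the events would be if counted. It does not show that the efficacy exclusion is wrong, since the documents do not say how the historical trials treated early failures.

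**The case against.** The strongest reply is that these events are not lost. The safety population keeps every treated subject and excludes no data (Section 9.1.3). Dilated ophthalmoscopy and BCVA are analysed safety endpoints (Section 9.4.7). First-week cases are labelled dropped subjects, and a disposition summary is planned (Section 9.4.1). The protocol defers safety evaluations to the SAP, which has the last word on statistical procedures (Sections 9.4.7 and 9.4.9). No separate SAP text is available here, so a suitable table may be defined there.

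Much of this stands. A reader might infer that the events reach no outcome table at all, and the documents do not support that. But none of these outputs is specified as a count of detachments, and none carries relatedness or time since injection. Week 24 attachment is a single time point, so an eye repaired earlier can appear attached.

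A reader might also infer that the DSMB would not learn of these events. That is not supported either: Section 3.4 leaves the content of its reviews to a charter that is not available, and nothing confines it to AE tables.

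A third tempting reading is that stable peripheral detachments are likewise shut out of efficacy. They are not. Section 2.2.1 says only that they are not primary failures. They fall outside the fovea-off or posterior-progression definition, so Section 8.2, read with the defined term, does not clearly bar them as AEs.

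Finally, Sections 8.2 and 8.6 can be read together. An SAE must first be an AE, the specific exemption can govern, and the example in 8.6 still has work to do for a fellow-eye detachment. That reading is available, but the text does not state it, and under it the first-week event remains unrecorded.

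**Conclusion.** The point holds for detachments in the first post-operative week that meet the imaging criteria. Following the protocol exactly, such an event in a treated eye is neither recorded as an AE or SAE nor counted for efficacy, and the available text plans no count of it as an event. Sections 8.2 and 8.6 also need to be reconciled. For stable peripheral detachments, the finding is only that their AE status is unclear.

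The size is one event without causality assessment or SAE report for each first-week detachment in a treated eye. The number cannot be derived from the documents; 2 to 10 per 100 treated eyes is an assumed range. The conclusion rests on reading recurrent detachment in Section 8.2 in line with the criteria in Section 2.2.1, and on there being no first-week detachment table in the SAP. Such a table would close the counting gap but would not restore causality assessment or expedited reporting.

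**What to change.** 1. **Section 8.2.** Limit the exemption to detachments that are counted as primary endpoint events. This would also cover a later detachment that the primary analysis leaves out: Section 9.4.5 limits the event to detachment attributed to PVR and requiring reoperation, and Section 8.2 has neither limit.
2. **Section 8.6.** Add a cross-reference so that the two sections agree. Other study-eye detachments, first-week events included, should be recorded as AEs and assessed for seriousness in the usual way. State how stable peripheral detachments are to be recorded.
3. **Section 9.4.7 and the SAP.** Add one safety-population listing or count of all study-eye detachments and reoperations, with timing relative to the most recent injection. State whether first-week subjects stay in the exploratory summaries.

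The imaging, visit dates and injection records needed are already collected. The cost is a wording amendment, one listing and a few more SAE reports. The primary analysis does not change. This is a cheap improvement.

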### **8.3. Recording Adverse Events**

Safety assessments will include but not limited to evaluation of AEs using National Cancer Institute's Common Terminology Criteria for Adverse Events (CTCAE) Version 5.0 2017, or higher, clinical laboratory results, pregnancy testing, and vital sign measurements. If a CTCAE grading is not listed for a specific event then the AE will be graded as mild, moderate or severe, per Section 8.4.

AEs will be recorded from the time of signing of informed consent up to the final clinical trial visit.

All AEs must be recorded in the site's clinical trial records and the AE eCRF. Investigators should use correct medical terminology when recording events and avoid abbreviations.

The investigator should attempt to establish a diagnosis of the AE based on signs, symptoms, and/or other clinical information. The diagnosis, and not the individual signs/symptoms, or laboratory abnormalities, should be documented in the subject's source documents and the eCRF unless the etiology of the event is unknown. If signs/symptoms cannot be medically characterized as a single diagnosis or syndrome at the time of reporting, each individual event should be recorded as an AE. If a diagnosis is subsequently established, it should be reported as follow-up information.

An assessment should be made at each visit (or more frequently if necessary) of any changes in severity, the suspected relationship to IP, the interventions required to treat it, and the outcome.

### **8.4. Assessment of Causality and Severity**

For each AE recorded, the investigator will make an assessment of causality and severity as follows:

1. Relationship to IP: The investigator must assess whether they consider an AE to be drug-related. In assessing this relationship, the investigator must use information about the drug as outlined in the Investigator's Brochure, the subject's pre-existent medical conditions/concurrent medication, and chronology of the event relative to drug administration. The following definitions will be used:
  - Definitely Related
  - Probably Related
  - Possibly Related
  - Unlikely to be related
  - Not Related

For regulatory authority reporting, only "related," or "not related" classification will be used. AEs identified as definitely, probably, or possibly, will be classified as "related." Those AEs identified as unlikely, or not related, will be classified as "not related."

2. Event Severity: The investigator will be asked to use their medical judgment to assess the severity of the AE.
3. The following are guidelines to be used by the investigator to judge the event severity of an AE:
  - Mild - awareness of sign or symptom, but easily tolerated
  - Moderate - discomfort enough to cause interference with usual activity
  - Severe - incapacitating with inability to work or perform usual activity
4. Expectedness: The expectedness of an AE should be determined based on upon existing safety information about the IP using the following explanations:
  - *Unexpected*: an AE that is not listed in the IB or is not listed at the specificity or severity that has been observed.
  - *Expected*: an AE that is listed in the IB at the specificity and severity that has been observed.
  - *Not applicable*: an AE unrelated to the IP.
  - AE events that are mentioned in the IB as occurring with a class of products or as anticipated from the pharmacological/mechanical (or other) properties of the product but are not specifically mentioned as occurring with the particular product under investigation, are to be considered unexpected.
  - The investigator should initially classify the expectedness of an AE, but the final classification is subject to the determination of the Sponsor's Medical Monitor.
5. Duration: Start and end dates and times, or if continuing.
6. Frequency: whether the event is a single episode, recurrent or continuous.
7. Action taken.
8. Whether it constitutes a SAE, per definition below.
9. Outcome: resolved, resolved with sequelae, continuing, death, or unknown (only for subjects that are lost to follow-up).

